7.5.3. Clinical Criteria for Monitoring for Potential Hepatic Decompensation Events

Subjects will be monitored for potential hepatic decompensation events throughout the study. Clinical criteria for the monitoring these events and the interruption/discontinuation of investigational product is summarized in [Table 5](#).

Investigational product should be discontinued permanently if the subject received a liver transplant or experiences multi-organ failure as defined in Table 5, Part A). Subjects should continue to return for scheduled study visits for safety follow up.

Subjects who experience other potential hepatic decompensation events defined in Table 5, Part B should be closely monitored until normalization or stabilization. Subjects may be rechallenged after a minimum of 30 days if fully resolved OR stable and approved by the Medical Monitor and Investigator.

Table 5: Clinical Criteria for Monitoring Potential Hepatic Decompensation Events and Interruption / Discontinuation of Investigational Product

A. Hepatic Decompensation Events Requiring Mandatory Discontinuation of Investigational Product	
Decompensation Event	Action Taken / Rechallenging Criteria
Liver Transplant	Discontinue IP permanently and follow patients until normalization/stabilization.
Multi-organ failure requiring hospitalization:	Continue to return for scheduled study visits for safety follow up.
B. Hepatic Decompensation Events Requiring Interruption of Investigational Product	

 • Liver failure defined as worsening synthetic function that is persistently worse relative to baseline and/or progressive over time (see Table 4, Part B)^a • Variceal bleeding or recurrent variceal bleeding^b documented by endoscopy or accompanied by anemia or melena with a hemoglobin drop of ≥ 2 g/dL • Ascites^c including: 
 ○ Worsening – requires increase in drug therapy or surgical intervention (paracentesis or shunt procedure) ○ Refractory ascites – unresponsive to medication; patient not candidate for transjugular intrahepatic portosystemic shunt (TIPS) or shunt; requires large volume paracentesis ○ Hyponatremia (≤ 125 mEq/L) secondary to ascites • Spontaneous Bacterial Peritonitis • Hepatic Encephalopathy, Grade ≥ 2 • Any liver-related event requiring hospitalization and treatment (except multi-organ failure) • Hepatorenal syndrome Type 1 or Type 2 and acute kidney injury, hepatopulmonary syndrome, or portopulmonary syndrome 	
Closely monitor until normalization or stabilization.
 
The patient may be rechallenged after a minimum of 30 days if fully resolved OR stable and approved by the Medical Monitor and Investigator
 
IP should be re-initiated at a lower dose (or lower dose frequency) and titrated per Investigator discretion.

^a Patients experiencing INR ≥ 2.0 unless due to vitamin K deficiency should be discontinued from IP permanently without rechallenge and should to return for scheduled study visits for safety follow up.

^b Endoscopic confirmation of gastric or duodenal varices without evidence of bleeding should be closely monitored; investigational product may be interrupted at Investigator discretion.

^c New onset ascites requiring treatment should be closely monitored; investigational product may be interrupted at Investigator discretion.

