Progress to CP B or C cirrhosis (CP score ≥7)	Adjust IP dose to 5 mg once weekly, then titrate to a maximum 10 mg twice weekly (at least 3 days apart).	After a minimum of 3 months, if at a lower dose, subjects may titrate to a maximum IP dose of 10 mg twice weekly per Investigator discretion.
New onset Severe Pruritus	Drug holiday or less frequent dosing	Return to original dose regimen if tolerated
DOSE INTERRUPTION		
Criteria	Action Taken with IP^a	Rechallenge^b
If liver biochemistries indicative of suspected hepatic injury are identified as exceeding upper threshold criteria and require immediate interruption (see Part A of Table 4) ^c	Interrupt immediately upon initial observation	Patient may be rechallenged after a minimum of 30 days if fully resolved OR stable and approved by the Medical Monitor and Investigator.

Table 7: Criteria for Dose Adjustment, Interruption, Discontinuation and Rechallenge (Continued)

Other liver biochemistries indicative of suspected hepatic injury are outside upper threshold criteria upon repeat testing as defined in Part A of Table 4 ^d	Interrupt after confirmation by repeat testing	
Liver biochemistries indicative of potential hepatic decompensation in the absence of symptoms (see Part B of Table 4) ^e	Closely monitor until normalization or stabilization. If values continue to increase relative to the baseline value, interrupt	
Clinical events indicative of hepatic decompensation (see Part B of Table 5)	Closely monitor until normalization	The subject may be rechallenged after a minimum of 30 days if fully resolved OR stable and approved by the Medical Monitor and Investigator. IP should be re-initiated at a lower dose (or lower dose frequency) and titrated per Investigator discretion.
Gastroenteritis (established severe abdominal pain, vomiting, diarrhea for more than 4 days)	Interrupt	If no evidence of liver injury is detected, IP may be restarted at the same dose after resolution of intercurrent illness.
Evidence of worsening of renal function or dehydration	Interrupt	
Pregnancy	Interrupt	Patient should continue with the study visit schedule. The subject may re-start IP when she is no longer pregnant or breastfeeding (if applicable) at the discretion of the Investigator and after discussion with the Medical Monitor
DOSE DISCONTINUATION		
Criteria	Action Taken with IP	Rechallenge

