If INR increases ≥ 2.0 in absence of clinical symptoms criteria (unless due to vitamin K deficiency)	Discontinue / No Rechallenge	Discontinue IP permanently and continue to return for scheduled study visits for safety follow up. Monitor closely for clinical outcomes per protocol. Continue to return for scheduled study visits for safety follow up. Monitor closely for clinical outcomes according to protocol assessments.
If total bilirubin, thresholds (Part B of Table 4) are observed in the presence of clinical symptoms of cholestatic hepatitis or hepatic encephalopathy ^f		
Multi-Organ failure requiring hospitalization		
Liver transplantation		

Fully resolved = Return to baseline levels or return to within normal limits (WNL). IP = investigational product

^a If subject is unable to be evaluated promptly, study drug must be immediately interrupted.

^b Requires complete documentation of complete resolution or normal/baseline results based on laboratory parameters and symptoms.

^c Total bilirubin baseline \leq ULN and Postbaseline $\geq 3x$ baseline, Baseline $>$ ULN and Postbaseline $\geq 2x$ Baseline, ALT or AST $> 3x$ baseline (and $>$ ULN)

^d ALT or AST $\geq 2x$ baseline, albumin < 3.2 g/L or electrolytes (sodium < 130 mEq/L).

^e Conjugated bilirubin > 0.5 mg/dL increase from baseline; Total bilirubin Baseline \leq ULN and 1.5 mg/dL increase from baseline OR Baseline $>$ ULN and 1.0 mg/dL increase from baseline; INR > 0.3 increase from baseline

^f If INR increases ≥ 2.0 in the absence of clinical symptoms or if conjugated bilirubin or total bilirubin, thresholds OR an INR increase from baseline of ≥ 1.5 are observed in the presence of clinical symptoms of cholestatic hepatitis or hepatic encephalopathy.

^g Multi organ failure including hepatorenal syndrome Type 1 or Type 2 and acute kidney injury, hepatopulmonary syndrome, or portopulmonary syndrome.

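### For hospitalized cases, Table 7 carries two overlapping rules on restarting product after hepatorenal, hepatopulmonary or portopulmonary syndrome, and does not say which prevails

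*Protocol*

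**What the plan says.** Two tables govern restart after clinical decompensation.

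**Section 7.5.3, Table 5.** The text above the table requires permanent discontinuation if a subject has a liver transplant or "experiences multi-organ failure as defined in Table 5, Part A". It then turns to the remaining events: "Subjects who experience other potential hepatic decompensation events defined in Table 5, Part B should be closely monitored until normalization or stabilization". Part B, as read, ends with the bullet "Hepatorenal syndrome Type 1 or Type 2 and acute kidney injury, hepatopulmonary syndrome, or portopulmonary syndrome". The bullet just before it reads "Any liver-related event requiring hospitalization and treatment (except multi-organ failure)". Footnote a to the liver-failure bullet says that subjects whose INR reaches 2.0 (vitamin K deficiency aside) "should be discontinued from IP permanently without rechallenge". For the other Part B events, rechallenge is possible after at least 30 days if the event has resolved or is stable, with approval from the Medical Monitor and the Investigator and at a lower dose or dosing frequency.

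**Section 7.6, Table 7.** The text makes this table the rule for any rechallenge. Its interruption section contains the row "Clinical events indicative of hepatic decompensation (see Part B of Table 5)", with the Part B restart conditions. The rechallenge column there carries footnote b, which asks for documented complete resolution, or normal or baseline results, on laboratory values and symptoms. Its discontinuation section contains the row "Multi-Organ failure requiring hospitalization", with no rechallenge. Footnote g reads "Multi organ failure including hepatorenal syndrome Type 1 or Type 2 and acute kidney injury, hepatopulmonary syndrome, or portopulmonary syndrome".

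Section 8.4 sends the reader to Section 7.6 for withdrawal after multi-organ failure.

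**The concern.** The syndromes in the last Part B bullet are the same as those in footnote g, in matching words. Through the interruption row they may be rechallenged. Through the discontinuation row, when the subject is hospitalized, they may not. Both rows sit in the one table that Section 7.6 makes operative, and the table gives no order of precedence between them.

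What is at stake is re-exposure after a severe hepatic event. Section 5.6 refers to a raised risk of decompensation and possibly higher hepatic exposure to the drug in this population. Section 5.7 reports post-marketing liver failure and death in patients with moderate to severe hepatic impairment, with causality not established. With about 170 sites (Section 8.1), two Investigators could reasonably reach different answers on the same kind of case. The Medical Monitor, who must approve any restart, would be working from the same ambiguous text.

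**Working it through.** No arithmetic applies, because the question is which rule governs which case. The two routes through Table 7 compare as follows.

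| | Interruption row, importing Table 5 Part B | Discontinuation row, read with footnote g |
|---|---|---|
| Syndromes named | Hepatorenal with acute kidney injury, hepatopulmonary, portopulmonary | The same |
| Hospitalization needed | Not stated | Yes |
| Product stopped | Yes, interrupted | Yes, permanently |
| Restart | Optional after at least 30 days, lower dose or frequency, two approvals, footnote b documentation | None |

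Applying both routes to the possible cases:

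1. **Syndrome without hospitalization.** Only the interruption row applies, because the other row requires hospitalization. There is no overlap.
2. **Hospitalized multi-organ failure in which one of the syndromes features.** The discontinuation row applies on any reading. The Part B bullet also matches on its face, because it has no exclusion.
3. **Isolated syndrome, hospitalized.** The Part B bullet matches. Whether the discontinuation row also matches depends on the word *including* in footnote g. It can mean that each named syndrome counts as multi-organ failure, or only that multi-organ failure may feature them. The protocol does not choose.

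Three features of the text bear on whether it resolves cases 2 and 3.

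- **The word *other* in Section 7.5.3.** It implies that Part B covers what Part A does not, so that discontinuation comes first. That is a sensible inference, but it stands in the text above Table 5, and Table 7 does not repeat it.
- **The neighbouring exclusions.** The liver-related hospitalization bullet excludes multi-organ failure explicitly, and footnote a sends INR of 2.0 or more to permanent discontinuation. The syndrome bullet has neither device. A hospitalized syndrome counted as multi-organ failure is excluded by one bullet and readmitted by the next.
- **Attachment of footnote g.** Its marker is not visible on the discontinuation row as read. Marker f is on the bilirubin row above, g is next in sequence, and its wording fits no other row. I take it as belonging to the multi-organ failure row.

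**The case against.** The strongest objection is layout. The multi-organ failure entry in Table 5 Part A ends in a colon as read, Section 7.5.3 says the definition is in Part A, and the last Part B bullet matches what follows *including* in footnote g. All three fit a list printed under Part A and displaced when the PDF was read. If that is so, Tables 5 and 7 agree and there is nothing to fix. This stands as a real possibility. As read, however, the bullet comes last in the Part B list, after that part's heading and its other bullets. For the same reason, a reader might infer that the protocol promises a definition in Part A and fails to give one. A bare colon in an extracted table cannot support that, and it is not claimed here.

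The second objection is that the text already gives a workable order: multi-organ failure requiring hospitalization goes to Part A, and other events go to Part B. This also stands in part. It defeats the stronger reading that the tables contradict each other for every case of these syndromes. Non-hospitalized cases have one rule, and hospitalized cases have a probable one. What it leaves is a precedence that has to be inferred and that the operative table does not state.

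The third objection is that restart is tightly controlled. Footnote b requires documented recovery, although that sits awkwardly beside a rule that also accepts a stable condition. Two approvals are needed. Section 12.1.5.1 has Investigators contact the Medical Monitor at any sign of decompensation, and an INR of 2.0 or more not due to vitamin K deficiency bars rechallenge independently. So a reader who infers that sites may restart product freely after these events would be wrong. The controls limit the consequence, but they do not tell the approvers whether a hospitalized case is eligible at all.

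**Conclusion.** The point holds in a limited form. As the tables are read, Table 7 gives two overlapping rules for a subject hospitalized with one of these syndromes: an optional, approved, lower-dose restart after at least 30 days, or no restart. The surrounding text leans towards no restart without saying so in the operative table.

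This is a minor-to-moderate patient-safety consistency point. Product stops under either rule, and no restart occurs without the Medical Monitor. The protocol gives no expected number of cases, so frequency cannot be stated; hepatorenal syndrome is an exclusion at entry (Section 8.3). A reader might look for an effect on the efficacy result. The documents support none: subjects who stop product stay in follow-up, and the primary analysis is by randomized treatment.

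The conclusion rests on two assumptions: that the syndrome bullet is printed in Part B, and that footnote g belongs to the multi-organ failure row.

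**What to change.** First check the printed layout of Table 5. If the syndrome list stands under Part A, no rule change is needed.

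If it stands in Part B:

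- Add to the syndrome bullet the limit *not meeting multi-organ failure requiring hospitalization*.
- State in Table 7 that the discontinuation row takes precedence over the interruption row, so that hospitalized cases of the syndromes named in footnote g are not rechallenged. Word it so that an isolated hospitalized syndrome is clearly covered, since *including* leaves that open. This follows the direction in which Section 7.5.3 already points, but it is a clinical rule that the sponsor's clinicians should confirm.

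The cost is a wording change in two tables and a letter to sites and the Medical Monitor, with no new procedures or data. The small downside is that some hospitalized subjects who recover could not restart product. They would remain in follow-up.

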7.5.4. Assessing Cirrhosis

7.5.4.1. Determination for Dosing Regimen

To determine which dosing regimen subjects should follow, the presence or absence of cirrhosis should be assessed by the Investigator at Screening Visit 1. Acceptable methods of confirming (via medical history) or assessing cirrhosis for purposes of determining dosing is defined as a

subject who has documented evidence or presence of one or more of the following cirrhosis indicators:

Biopsy results consistent with PBC Stage 4 ([Ludwig 1978](#))

- TE Median Value ≥ 16.9 kPa ([Corpechot 2012](#))
- The presence of any of the following (unless exclusionary per [Section 8.3](#)) in the absence of acute liver failure:
 - Varices
 - Ascites
 - Radiological evidence of cirrhosis (nodular liver or enlargement of portal vein and splenomegaly)
- Combined low platelet count ($<140\,000/\text{mm}^3$) with:
 - persistent decrease in serum albumin, or
 - elevation in prothrombin time /INR (not due to antithrombotic agent use), or
 - elevated bilirubin ($2\times$ ULN)

Subjects who exhibit no evidence of cirrhosis by the above methods of assessment will be dosed using the Standard Dosing Regimen, while those who do exhibit evidence of cirrhosis by one or more of the above methods will be dosed using the Modified Dosing Regimen according to their Child-Pugh Score calculated in the electronic case report form (eCRF) (see [Appendix A](#) and [Section 7.3](#)).

Cirrhosis status should be reassessed as clinically indicated throughout the study. Any change in cirrhosis status will necessitate re-evaluation of the dosing regimen.

7.5.4.2. Progression to Cirrhosis

When a subject identified as noncirrhotic at Baseline per the criteria listed in [Section 7.5.4](#) exhibits any signs or symptoms associated with progression to cirrhosis, as defined by the same criteria, the subject should also be assessed by Fibroscan® TE where available and progression to cirrhosis confirmed by biopsy (centrally read) unless not medically indicated. Laboratory samples needed to obtain noninvasive scores of liver fibrosis (ELF, and aspartate aminotransferase to platelet ratio index [APRI]) will also be collected when a subject develops evidence of progression to cirrhosis.

Full instructions concerning the sample collection methods, processing, labeling, and shipping will be provided by the Sponsor in a study-specific histology manual. Collection supplies will be provided by the central laboratory.

Sites participating in the paired biopsy substudy must confirm progression to cirrhosis by biopsy as per the information outlined in protocol Addendum 2.

All suspected cases of progression to cirrhosis should be submitted for adjudication regardless of the availability of transient elastography or biopsy results.

7.5.5. Child-Pugh Score

Child-Pugh (CP) Score ([Pugh 1973](#), [Lucey 1997](#)) is calculated and reported within the EDC system based on data entered into the eCRF by adding the scores from the 5 factors outlined in Table 6 and can range from 5-15. Although CP score calculation will automatically be computed in all subjects, it should only be applied to subjects who meet criteria for progression to cirrhosis. Dose adjustment or discontinuation should not be considered based solely on the CP score, in subjects who do not meet criteria for presence of cirrhosis.

A total score of 5-6 is considered Grade A (mild, well compensated disease); 7-9 is Grade B (moderate, significant functional compromise); and 10 and above is Grade C (severe, decompensated disease). Sponsor calculation of the CP Score includes Investigator assessments of ascites and hepatic encephalopathy, which may be assessed during the adverse event review at the scheduled visits, as well as total bilirubin, serum albumin, and prothrombin time, which will populate from the central laboratory.

Table 6: Child-Pugh Scoring System

Factor	Units	Points		
		1	2	3
Serum bilirubin	µmol/L	<34	34-50	>50
	mg/dL	<2.0	2.0-3.0	>3.0
Serum albumin	g/L	>35	28-35	<28
	g/dL	>3.5	2.8-3.5	<2.8
Prothrombin time	Seconds prolonged	0-3	4-6	>6
	INR	<1.7	1.7-2.3	>2.3
Ascites	NA	None	Mild	Moderate-Severe
Hepatic encephalopathy ^a	NA	No	Grade 1 or 2	Grade 3 or 4

INR = international normalized ratio; NA=not applicable

^a Grade 0: normal consciousness, personality, neurological examination, electroencephalogram
 Grade 1: restless, sleep disturbed, irritable/agitated, tremor, impaired handwriting, 5 cps waves
 Grade 2: lethargic, time-disoriented, inappropriate, asterixis, ataxia, slow triphasic waves
 Grade 3: somnolent, stuporous, place-disoriented, hyperactive reflexes, rigidity, slower waves
 Grade 4: unrousable coma, no personality/behavior, decerebrate, slow 2-3 cps delta activity
 Child-Pugh criteria: [Pugh 1973](#), [Lucey 1997](#), [Vilstrup 2014](#).

7.5.5.1. Mayo Risk Score

Mayo Risk Score (MRS) ([Dickson 1989](#)) is calculated and reported within the EDC system based on data entered into the eCRF. Calculation of MRS includes Investigator assessment of peripheral edema and the use of diuretic therapy, which will be assessed during adverse event and concomitant medicine review at the scheduled visits and entered into the eCRF, as well as total bilirubin, albumin, and prothrombin time results obtained from the central laboratory data.

7.6. Dose Adjustment, Interruption, and Withdrawal from Investigational Product or Study

Investigational product may be temporarily decreased (eg, from 10 mg twice weekly to 5 mg twice weekly, or from 5 mg twice weekly to 5 mg once weekly) or temporarily or permanently stopped based on safety and/or tolerability concerns. Investigational product may be resumed at the maintenance dose upon resolution of gastroenteritis or worsening renal function or dehydration if there is no evidence of liver injury. For rechallenge, following all other dose interruptions (see Table 7), investigational product should be initiated at a lower dose and subjects monitored more frequently with up-titration considered based on tolerability.

Adjustments, interruptions, discontinuation, and any rechallenge of investigational product should be implemented per the criteria outlined in Table 7. Subjects who discontinue investigational product are expected to continue in the study (and follow the regular visit schedule) until the end of the study, and the study will terminate at the time when the needed number of adjudicated events has accrued. If a subject reaches an outcome event, he or she should continue the regular visit schedule and continue taking investigational product as long as the subject has not met any of the criteria for mandatory interruption of investigational product outlined in Table 7, and the Investigator assesses it as safe to continue. In general, subjects should be strongly encouraged to both stay on investigational product and remain in the study until study termination. If a subject discontinues investigational product and cannot continue to attend regularly scheduled study visits, the subject should be strongly encouraged to participate in study follow-up via phone calls or electronic medical record review as described in [Section 7.9](#).

Table 7: Criteria for Dose Adjustment, Interruption, Discontinuation and Rechallenge

DOSE ADJUSTMENT		
Criteria	Action Taken with IP	Adjustment
Progress to cirrhosis and have CP A cirrhosis (CP score <7)	Adjust to a maximum daily dose of 10 mg (or equivalent placebo) in a blinded fashion	Not applicable. Remain at maximum daily dose of 10 mg (or equivalent placebo) for remainder of study.
Progress to CP B or C cirrhosis (CP score ≥7)	Adjust IP dose to 5 mg once weekly, then titrate to a maximum 10 mg twice weekly (at least 3 days apart).	After a minimum of 3 months, if at a lower dose, subjects may titrate to a maximum IP dose of 10 mg twice weekly per Investigator discretion.
New onset Severe Pruritus	Drug holiday or less frequent dosing	Return to original dose regimen if tolerated
DOSE INTERRUPTION		
Criteria	Action Taken with IP^a	Rechallenge^b
If liver biochemistries indicative of suspected hepatic injury are identified as exceeding upper threshold criteria and require immediate interruption (see Part A of Table 4) ^c	Interrupt immediately upon initial observation	Patient may be rechallenged after a minimum of 30 days if fully resolved OR stable and approved by the Medical Monitor and Investigator.

Table 7: Criteria for Dose Adjustment, Interruption, Discontinuation and Rechallenge (Continued)

Other liver biochemistries indicative of suspected hepatic injury are outside upper threshold criteria upon repeat testing as defined in Part A of Table 4 ^d	Interrupt after confirmation by repeat testing	
Liver biochemistries indicative of potential hepatic decompensation in the absence of symptoms (see Part B of Table 4) ^e	Closely monitor until normalization or stabilization. If values continue to increase relative to the baseline value, interrupt	
Clinical events indicative of hepatic decompensation (see Part B of Table 5)	Closely monitor until normalization	The subject may be rechallenged after a minimum of 30 days if fully resolved OR stable and approved by the Medical Monitor and Investigator. IP should be re-initiated at a lower dose (or lower dose frequency) and titrated per Investigator discretion.
Gastroenteritis (established severe abdominal pain, vomiting, diarrhea for more than 4 days)	Interrupt	If no evidence of liver injury is detected, IP may be restarted at the same dose after resolution of intercurrent illness.
Evidence of worsening of renal function or dehydration	Interrupt	
Pregnancy	Interrupt	Patient should continue with the study visit schedule. The subject may re-start IP when she is no longer pregnant or breastfeeding (if applicable) at the discretion of the Investigator and after discussion with the Medical Monitor
DOSE DISCONTINUATION		
Criteria	Action Taken with IP	Rechallenge
If INR increases ≥ 2.0 in absence of clinical symptoms criteria (unless due to vitamin K deficiency)	Discontinue / No Rechallenge	Discontinue IP permanently and continue to return for scheduled study visits for safety follow up. Monitor closely for clinical outcomes per protocol. Continue to return for scheduled study visits for safety follow up. Monitor closely for clinical outcomes according to protocol assessments.
If total bilirubin, thresholds (Part B of Table 4) are observed in the presence of clinical symptoms of cholestatic hepatitis or hepatic encephalopathy ^f		
Multi-Organ failure requiring hospitalization		
Liver transplantation		

Fully resolved = Return to baseline levels or return to within normal limits (WNL). IP = investigational product

^a If subject is unable to be evaluated promptly, study drug must be immediately interrupted.

^b Requires complete documentation of complete resolution or normal/baseline results based on laboratory parameters and symptoms.

^c Total bilirubin baseline \leq ULN and Postbaseline $\geq 3x$ baseline, Baseline $>$ ULN and Postbaseline $\geq 2x$ Baseline, ALT or AST $> 3x$ baseline (and $>$ ULN)

^d ALT or AST $\geq 2x$ baseline, albumin < 3.2 g/L or electrolytes (sodium < 130 mEq/L).

^e Conjugated bilirubin > 0.5 mg/dL increase from baseline; Total bilirubin Baseline \leq ULN and 1.5 mg/dL increase from baseline OR Baseline $>$ ULN and 1.0 mg/dL increase from baseline; INR > 0.3 increase from baseline

^f If INR increases ≥ 2.0 in the absence of clinical symptoms or if conjugated bilirubin or total bilirubin, thresholds OR an INR increase from baseline of ≥ 1.5 are observed in the presence of clinical symptoms of cholestatic hepatitis or hepatic encephalopathy.

^g Multi organ failure including hepatorenal syndrome Type 1 or Type 2 and acute kidney injury, hepatopulmonary syndrome, or portopulmonary syndrome.

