8.4.1. Other Reasons for Discontinuation of Study or Investigational Product

In general, the site should counsel the subject on the importance of maintaining the regular visit schedule and remaining on investigational product. Subjects should be strongly encouraged to both stay on investigational product and remain in the study until study termination. Subjects who discontinue investigational product prior to termination of the study need to also continue to follow the regular visit schedule through to study closure. With the exception of liver transplant, if a subject experiences a suspected or confirmed clinical outcomes event, he or she should continue the regular visit schedule and continue taking investigational product as long as the Investigator assesses it as safe. Specific strategies to encourage continued subject participation in the study will be outlined in a Subject Retention Plan. Subjects who discontinue investigational product, but agree to follow up either through phone calls or review of electronic medical records are expected to continue to provide information regarding clinical outcomes or new interventions for PBC (such as initiating commercial OCALIVA). Early termination procedures should only be conducted if the subject withdraws consent (see [Section 9.7.15](#)).

The following events are considered appropriate reasons for a subject to discontinue investigational product; however, these subjects are expected to continue in the study until study termination (or at the discretion of the Sponsor):

- Subject begins treatment with commercially available OCALIVA.
 - If a subject begins treatment with commercially available OCALIVA, they must interrupt IP immediately and this must be reported in the treatment discontinuation eCRF to prevent double dosing and for notification of the sponsor and medical monitor.
- The Investigator or Sponsor considers that it is advisable or in the best interest of the subject.
- The occurrence of clinical or laboratory AEs considered by the Investigator to be clinically important safety concerns and related to study drug.
- Withdrawal of consent:
 - Consent may be fully withdrawn (in which case the subject discontinues both investigational product and study visits and procedures).

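### Clinical decompensation events are classed as requiring interruption of product, but the action stated for them is only close monitoring, and the rules for continuing product after an outcome event differ between sections

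*Protocol*

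**What the plan says.** **Classification.** Section 7.5.3, Table 5 Part B carries the heading "B. Hepatic Decompensation Events Requiring Interruption of Investigational Product". It lists variceal bleeding, spontaneous bacterial peritonitis, hepatic encephalopathy of grade 2 or more, worsening or refractory ascites, liver failure, hepatorenal and related syndromes, and any other liver-related event needing hospitalization and treatment. Section 7.6, Table 7 repeats these events in a row beginning "Clinical events indicative of hepatic decompensation (see Part B of Table 5", inside the block "DOSE INTERRUPTION".

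**Action.** The Table 5 Part B cell opens with "Closely monitor until normalization or stabilization". The section 7.5.3 text says: "Subjects who experience other potential hepatic decompensation events defined in Table 5, Part B should be closely monitored until normalization or stabilization". The Table 7 action cell also says to monitor closely, with normalization alone as the end point.

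**Rechallenge.** Both tables set a minimum of 30 days before rechallenge, require Medical Monitor and Investigator approval, and call for a restart at a reduced dose or frequency.

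**Continuing after an outcome event.** Section 7.6 allows continued dosing "as long as the subject has not met any of the criteria for mandatory interruption of investigational product outlined in Table 7", and if the Investigator also judges it safe. Section 8.4.1, with liver transplant excepted, says the subject should "continue taking investigational product as long as the Investigator assesses it as safe". Section 7.1 and the synopsis make continuation depend only on the protocol's discontinuation criteria.

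**The concern.** A site managing a variceal bleed or an episode of encephalopathy will look for the action column. For these events that column does not say to stop product, although the heading above it says that interruption is required. A site working from the action cell could go on dosing, and a site working from the heading would stop. The sections on continuing after an outcome event do not settle the matter, because they apply different tests.

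These are among the most serious hepatic events in the trial. Section 5.6 itself cites elevated decompensation risk and possibly higher hepatic exposure as reasons for closer monitoring. Follow-up intensity also turns on the reading: section 7.7 attaches contact at least every 2 weeks and visits every 6 weeks to interruption or discontinuation. Exposure after a first decompensation, before any later transplant or death, could therefore vary by site.

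**Working it through.** No figure in the protocol bears on this point, so the check is a comparison of the current Version 6 text.

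**1. Actions in the Table 7 interruption block**

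| Criterion (paraphrased) | Action on product |
|---|---|
| Liver biochemistry above the upper threshold | Interrupt at once |
| Other biochemistry, on repeat testing | Interrupt once confirmed |
| Biochemical decompensation without symptoms | Monitor; interrupt if values keep rising |
| Clinical decompensation events (Table 5 Part B) | Monitor closely |
| Gastroenteritis | Interrupt |
| Worsening renal function or dehydration | Interrupt |
| Pregnancy | Interrupt |

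Six of the seven rows say to interrupt or when to. The clinical decompensation row does neither, although the laboratory-only row directly above it states when to interrupt.

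**2. Whether other text supplies the missing instruction**

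- The rechallenge text presupposes that product was stopped, but does not order the stop.
- Table 5 footnotes b and c leave interruption to the Investigator for non-bleeding varices and for new-onset ascites. Singling these out suggests that the other Part B events were meant to be handled differently. That is an inference.
- Table 7 footnote a requires immediate interruption only where the subject cannot be evaluated promptly.
- The section 7.5.3 sentence on Part B repeats the monitoring instruction.

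**3. Continuing product after an outcome event**

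| Place | Condition for continuing |
|---|---|
| Section 7.6 | No Table 7 mandatory-interruption criterion met, and Investigator judges it safe |
| Section 8.4.1 | Investigator judges it safe (transplant excepted) |
| Section 7.1 and synopsis | No discontinuation criterion met |

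A Part B event is classed under interruption, not discontinuation. By itself it therefore does not end dosing under section 7.1 or the synopsis. Section 8.4.1 leaves the decision to the Investigator. Section 7.6 refers to Table 7, where the relevant row has no interruption action, so the reference does not resolve the question.

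**4. Overlap with the primary endpoint (section 13.1.3)**

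Hospitalization of 24 hours or more for variceal bleed, hepatic encephalopathy or spontaneous bacterial peritonitis is a primary component, and all three conditions are in Part B. Refractory ascites in Part B is close to the uncontrolled-ascites component, but the definitions differ. The same clinical event can therefore fall under both the Part B text and the continuation rules.

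**The case against.** The strongest reply is that the protocol, read as a whole, supports one reading and that a single word has dropped out of two cells. The Part B heading, the Table 7 block title, the 30-day minimum with restart at a lower dose, and the discretionary exceptions in footnotes b and c all point the same way. Section 7.7 prescribes close monitoring for subjects whose product has been interrupted, so the cell may describe what follows interruption rather than replace it. Most of this stands as evidence of drafting intent, and it would be too strong to call the question wholly open. It does not remove the defect, because the instruction must still be inferred.

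A reader might also infer that section 8.4.1 tells sites to dose through decompensation. The documents do not support that. The sentence depends on the Investigator's safety judgement and excepts transplant, and the parent section 8.4 refers decompensation to section 7.6, leaving 8.4.1 to deal with other reasons. What remains is that 8.4.1, section 7.1 and the synopsis do not carry the interruption condition that section 7.6 does.

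Nor do sites act alone. Sections 7.5.1, 7.7 and 12.1.5.1 bring in the Medical Monitor, and rechallenge needs the Medical Monitor's approval. This should limit divergence but does not supply the missing instruction.

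Finally, a reader might infer damage to the primary analysis. That analysis is time to first event in the ITT population, and subjects who stop product stay in follow-up. Dosing after a qualifying event cannot move that subject's primary event time.

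**Conclusion.** The point holds as an internal inconsistency in safety-relevant instructions. The classification of these events and the action stated for them disagree in Table 5 Part B and Table 7, and the continuation rule takes three forms. Its extent in the text is one of seven rows in the Table 7 block, the matching Table 5 cell and the section 7.5.3 sentence. It touches three primary-endpoint conditions directly and a fourth, ascites, approximately. The number of subjects or events affected is not given and cannot be derived.

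The main consequence is for patient safety. The primary analysis is largely unaffected; the qualification is that some Part B events, such as a variceal bleed without a 24-hour stay, are not primary events and could precede one. Possible secondary effects are on post-event exposure, on safety summaries, and on later events such as transplant or death, which form a key secondary endpoint. These effects assume that sites do read the passages differently, which the documents cannot show. No view is taken on which clinical rule is right.

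**What to change.** Reconcile seven places so that one instruction applies to the Part B events:

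- Table 5 Part B (heading and action cell);
- the section 7.5.3 text on Part B;
- the matching Table 7 row, including its monitoring end point, which differs from Table 5;
- the outcome-event sentence in section 7.6;
- the corresponding sentence in section 8.4.1;
- the corresponding sentence in section 7.1;
- the corresponding sentence in the synopsis.

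The last four should cross-refer to Table 7 rather than each state a separate condition. The sponsor's clinical team must decide which instruction is intended.

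The cost is protocol wording, the usual review of an amendment, and a memo to sites. The sample size, endpoints and planned analyses need no change.
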